8.2.3. Follow-up of AE and SAE

The main adverse events (AEs) discerned during the 180 day follow-up interviews will be suicidal ideation with intent, or a recent suicide attempt. All AEs and SAEs will be documented

by the site manager and will be reported to the DSMB and IRB as needed. [name] will be notified because part of his role as overall PI of all AEs and SAEs.

8.2.4. Regulatory Reporting Requirements for SAE

- Prompt notification by the investigator to the sponsor of SAE is essential so that legal obligations and ethical responsibilities towards the safety of participants and the safety of a study treatment under clinical investigation are met.
- The sponsor has a legal responsibility to notify both the local regulatory authority and other regulatory agencies about the safety of a study treatment under clinical investigation. The sponsor will comply with country-specific regulatory requirements relating to safety reporting to the regulatory authority, Institutional Review Boards (IRB)/Independent Ethics Committees (IEC), and investigators.
- The Institutional Review Boards of each site will be responsible for monitoring risks to human subjects and assessment of ethical issues related to this study, and will have approved the consent form and protocol prior to initiation of the study. The consent form will be scripted to minimize burden and stress. All unexpected AEs and SAEs will be reported to the IRB's per institutional and regulatory requirements as well as the DSMB. If the AEs and SAEs are related to study procedures, then we will review with the DSMB. This will be part of our safety monitoring and DSMB charter.
- Overall data monitoring will be the responsibility of the PIs. During the course of the study, the PIs will follow the progress of the clinical study and data entry to ensure utmost accuracy of the data and to detect any possible errors at an early time point. The research coordinators will generate weekly reports, which will include suicidality, and adverse events for each subject for review during weekly project meetings as well as an ongoing CONSORT diagram. DSMB reports will include recruitment data, demographic information, serious adverse events, early termination, and protocol deviations, as well as any other information requested by the DSMB.

9. Statistical Considerations

9.1. Sample Size Determination

We proposed to recruit approximately 244 eligible cases that will be followed in three treatment arms: telehealth CIS, in-person OCIC, and inpatient. We expect that the sample sizes for the three arms will be *at least* 75, 75, and 70 respectively. These numbers account for an expected 10 % dropout rate; 220 participants are expected to complete study procedures. Prior evidence suggests that the 6-month inpatient readmission rate for adolescents with a prior history of suicidality is approximately 19%.¹⁰⁸ Preliminary data suggest that almost 10% of adolescents who received OCIC treatment following a suicidal event could have recurrent suicidal attempts during the following 6 months after OCIC treatment (preliminary unpublished data from the sites from Dallas and Cincinnati). Therefore, if we assume the hazard ratio (inpatient group vs. OCIC group) will be approximately 2.8 and the readmission rates over 6 months for the two groups will be 19% (for the inpatient group) vs. 10% (for the OCIC group), we will be able to achieve the statistical power at 0.70 given the two-side alpha value = 0.05. We expect numbers for the

Telehealth CIS to be larger than the inpatient group. We will achieve similar power when we compare the Telehealth CIS group with the inpatient group. The power is likely lower than 0.6 when we compare Telehealth CIS with the OCIC group since the effect size (i.e., hazard ratio < 2). The power calculation, based on the assumption that 19% (inpatient group) vs. 10% (Telehealth CIS or OCIC group) will be the averaged recurrence rates for the two arms across the four sites, was performed using the powerSurvEpi package in the software R. For continuous outcomes, we expect that the two-group comparison can achieve the power at 0.84 when the effect size Cohen's d is 0.5 and sample sizes for the first and second group are 75 and 70, respectively. Alternatively, we will achieve the power at 0.76 if we use ANOVA to evaluate whether the continuous outcome differs among the three groups given the effect size $f^2 = 0.2$

For purposes of analysis, the following populations are defined:

Population	Description
Enrolled	All participants who sign the ICF
Observational	All patients will be followed in three treatment arms (telehealth CIS, in-person OCIC, and inpatient)
Evaluatable	Inclusion: 1) Adolescents (12 to 18 years old) who were brought to the ED due to suicidal thoughts or behaviors and require a higher level of care (Telehealth, OCIC or inpatient); 2) The presence of a legal guardian. Exclusion: 1) Adolescents with suicidal thoughts who had prior OCIC treatment in the past 12 months will be excluded; 2) Adolescents without the ability to answer survey questions will be excluded.
Safety	Participants will be analyzed according to the treatment they actually received.

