2.2. Background

Suicide is a leading cause of death for adolescents in the United States.¹⁻⁵ Adolescent suicidality includes suicidal thoughts, intent, plans, and attempts.⁷³ Suicidality does not include nonsuicidal self-injury (NSSI) because it does not include intent to die.⁷⁴ The primary outcome measure for this proposed research will be the time to first recurrence of a suicidal event.⁷⁵ A suicidal event is defined as: a suicide attempt, interrupted attempt, hospitalization because of suicidal risk, an emergency/urgent evaluation because of suicidal risk, and a death by suicide. NSSI is not our primary target and we will focus on adolescents who present with suicidal thoughts and suicide attempts which can also include NSSI. Therefore, to improve generalizability, we will collect data on NSSI even though it is not part of our primary outcome.

Our stakeholder partner, [name], Executive Director, NAMI of Southwest Ohio, clarified that the most acceptable terminology is death by suicide or died by suicide rather than committed or completed suicide.⁷⁶ For adolescents in the United States in 2015, suicide was the third leading cause of death between the ages of 10 and 14, and the second leading between the ages of 15 and 34.^{2, 4, 5} For girls (ages 15 to 19), the suicide rate doubled from 2007 to 2015 and was at its highest peak in 40 years in 2015 with a rate of 5.1 per 100,000. For males (ages 15 to 19), the suicide rate increased by 31% between 2007 and 2015 when the rate was 14.2 per 100,000.³ The Youth Risk Behavior Surveillance Survey estimated that of high school students, 16% reported seriously considering suicide, 13% reported creating a plan to kill themselves, and 8% reported trying to kill themselves in the previous 12 months.⁷⁷ Adolescent suicidal behavior is common, with more than 1 million attempts and 4,600 deaths by suicide each year.⁵² There is a clear need for development of treatment programs both aimed at preventing adolescent suicide attempts, as well as addressing recurrent suicidal ideation and promotion of safety following an attempt.^{78, 79}

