Scores on the CHRT were also significantly reduced by discharge with propensity scores (26.01 ± 10.43 vs. 16.72 ± 10.03 ; $p < .0001$) as well as active suicidal ideation scores (4.85 ± 3.63 vs. 1.91 ± 2.40 ; $p < .0001$) showing a marked improvement compared to baseline. Preliminary clinical outcomes at discharge from [name]'s OCIC and at six month follow-up were positive. Patients were improved at the time of discharge on self-report of depressive symptoms

and suicidal ideation and behavior. 286 of the 364 adolescents (or 78.57%) responded to the 6 month follow up questions. In total, 8.7% and 27.3% of the 286 respondents reported a suicide attempt and event, respectively, within 6 months of discharge from OCIC. Reattempt rates at 6 months were at 8.7%, with almost half these occurring within one month after discharge. Suicidal events (includes attempts, emergency room visits or hospitalization) at 6 months were at 27.3%. It is possible that the suicidal events were higher than attempts because the adolescents were following their safety plan and reaching out for professional support when suicidal ideation increases. Patients who made an attempt within the 6 month follow up period had a history of more previous attempts, higher self-report of depressive symptoms at discharge, and higher levels of active suicidal ideation (CHRT) at entry and exit.

Those patients who had a suicide event at follow-up were more likely to be female, had more previous attempts, and had higher self-reported and parent reported depression at entry in the program. Those with a suicidal event also had higher self-reported active suicidal ideation at entry into the program.

Due to the fact that telehealth CIS is only currently being widely used for mental health services in this population group, CHRT-SR and other follow up data is not currently known. This research will seek to fill in this gap of knowledge.

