Breach of confidentiality: There is a potential risk of loss of confidentiality. Consistent with the Federal guidelines, all patients and guardians will be informed of the federally mandated reporting laws for child abuse and neglect, verbally and in the written consent form. Therefore, if abuse or neglect is suspected, per institutional and legal standards and requirements, the Department of Human Services may be called if appropriate and indicated. Risks associated with this reporting include embarrassment, legal consequences, and removal of the child from home.

3. Specific Aims and Hypothesis

Specific Aims	Hypothesis

SA1: Evaluate the safety of CIS-telehealth relative to inpatient and OCIC-in-person among children with similar CHRT-SR scores.
	
 Our working hypothesis is that CIS-telehealth is associated with a greater risk of suicidal event relative to inpatient and in-person OCIC. Response is defined by a delay in first recurrence of a suicidal event and a lower number of suicidal events over 90 days and 180 days. Clinical Features: 
 Severity of suicidal ideation at baseline and over 180 days number of suicidal events at baseline only Substance use at baseline and over 180 days. Sociodemographic features: Age, Gender, Gender Identity, Type of insurance (Public, Private or none), Ethnicity, Race, or living with one biological parent, two biological parents, a stepparent, a relative, or other.

SA2: Examine the effectiveness of CIS-telehealth relative to inpatient and in-person OCIC among children with similar CHRT scores.
	
 Our working hypothesis is that CIS-telehealth will be associated with poorer reduction in emotional arousal and perceived stress levels in response to COVID-19 the pandemic relative to CIS-inpatient and CIS-in-person.

SA3: Assess patient and parent treatment satisfaction with CIS-telehealth relative to inpatient and in-person OCIC among children with similar CHRT scores.
	
 Our working hypothesis is that CIS-telehealth is associated with less patient satisfaction than inpatient and in-person OCIC among children with similar CHRT scores.

Exploratory Aim
	

[figure not shown]
Specific Aims	Hypothesis

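### The power statement for the primary endpoint pairs an inpatient readmission rate with an OCIC suicide-attempt rate; neither is the composite suicidal event, and the rate assumed for telehealth does not match SA1

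*Combined protocol and SAP*

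**What the plan says.** Section 2.2 defines the event behind the primary endpoint: "A suicidal event is defined as: a suicide attempt, interrupted attempt, hospitalization because of suicidal risk", and it goes on to include emergency or urgent evaluation for suicidal risk and death by suicide. Section 9.2.1 makes time to first recurrence of such an event the primary outcome, analysed with a Cox model.

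Section 9.1 takes its planning rates from two sources:
- Inpatient: "Prior evidence suggests that the 6-month inpatient readmission rate for adolescents with a prior history of suicidality is approximately 19" percent.
- OCIC: "almost 10% of adolescents who received OCIC treatment following a suicidal event could have recurrent suicidal attempts during the following 6 months".

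It then continues "if we assume the hazard ratio (inpatient group vs. OCIC group) will be approximately 2.8 and the readmission rates over 6 months", with 19% and 10% as the two rates, and concludes "we will be able to achieve the statistical power at 0.70 given the two-side alpha value = 0.05". Further on, 19% (inpatient) and 10% (telehealth or OCIC) are described as recurrence rates averaged over the four sites.

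The preliminary data in Section 2.2 report both outcomes for the Dallas OCIC at 6 months, among 286 respondents of 364 patients. Attempts were 8.7%, and "Suicidal events (includes attempts, emergency room visits or hospitalization) at 6 months were at 27.3" percent.

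Section 3 (SA1) states: "Our working hypothesis is that CIS-telehealth is associated with a greater risk of suicidal event relative to inpatient and in-person OCIC".

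Sections 4.2 and 9.2.3 repeat the claim of power above 0.70 at HR 2.8, but for an Aim 1 analysis of recurrence within 3 months.

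**The concern.** The two planning rates do not measure the same thing. The inpatient rate counts readmissions, and Section 9.1 does not say they are restricted to suicidal risk. The OCIC rate counts attempts. Each is close to one component of the composite, but a different component in each arm. A contrast between them can therefore reflect the choice of outcome as much as the treatment setting. Using one label for both hides this.

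This paragraph is the only justification of the sample size for the primary safety endpoint. If the study finds no difference between arms, readers will turn to the stated power to judge what could have been detected. A figure built on other outcomes cannot tell them.

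The assumed direction raises a second question. The safety aim expects telehealth to carry more risk than inpatient care and OCIC. Section 9.1 gives telehealth roughly half the inpatient rate and the same rate as OCIC, so no calculation addresses the effect that SA1 hypothesises.

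**Working it through.** **Inputs.** From 9.1: 6-month rates 19% and 10%, HR 2.8, arms 75 (telehealth), 75 (OCIC) and 70 (inpatient), two-sided alpha 0.05. From 2.2: OCIC suicidal events 27.3% at 6 months; Cincinnati OCIC, 25 of 401 back in the ED for psychiatric reasons within 90 days. No inpatient composite rate is given.

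**Formulas.** With m events:
- HR implied by two rates = ln(1−p1)/ln(1−p0); rate implied by an HR: p1 = 1−(1−p0)^HR.
- Schoenfeld power = Φ(√(m·a·(1−a))·|ln HR| − 1.96), with a the share of patients in one arm.
- Freedman-type power = Φ(√(k·m)·|HR−1|/(k·HR+1) − 1.96), with k the ratio of arm sizes.

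**The plan's own figure.** Events = 70×0.19 + 75×0.10 = 20.8. At HR 2.8, power is 0.59 (Freedman) to 0.65 (Schoenfeld), against the stated 0.70. The two rates imply HR = ln(0.81)/ln(0.90) = 2.0, for which power is 0.34 to 0.35. This is a separate discrepancy; correcting it would leave the outcome mismatch in place.

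**What the assumed effect needs on the composite.** With OCIC at 27.3%:
- HR 2.8 needs 1−0.727^2.8 = 59.0% inpatient.
- HR 2.0 needs 1−0.727^2 = 47.1% inpatient.
- An assumed inpatient rate of 30% gives HR 1.1, and 40% gives HR 1.6.

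**A low end for OCIC.** 25/401 = 6.2% at 90 days. At constant hazard, 1−(1−0.0623)² = 12% at 6 months. This counts ED returns only, for any psychiatric reason, so it is not the full composite.

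**Power for inpatient vs OCIC (70 vs 75), 6-month rates, Freedman to Schoenfeld:**

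| OCIC rate | HR | Inpatient rate | Events | Power |
|---|---|---|---|---|
| 27.3% | 1.5 | 38.0% | 47.1 | 0.28 |
| 27.3% | 2.0 | 47.1% | 53.5 | 0.69–0.72 |
| 27.3% | 2.8 | 59.0% | 61.8 | 0.97–0.98 |
| 12% | 1.5 | 17.4% | 21.2 | 0.15 |
| 12% | 2.0 | 22.6% | 24.8 | 0.39–0.41 |
| 12% | 2.8 | 30.1% | 30.1 | 0.75–0.81 |

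**SA1 direction, telehealth worse than OCIC (75 vs 75).** With OCIC at 27.3%, power is 0.29 at HR 1.5, 0.70–0.74 at HR 2.0 and 0.97–0.985 at HR 2.8.

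**Window.** If the analysis stops at 3 months and the hazard is constant, 27.3% becomes 1−√0.727 = 14.7%. Power for 70 vs 75 then falls to 0.18, 0.46–0.48 and 0.83–0.87 at the same three HRs. Section 2.2 reports that almost half of the reattempts fell in the first month after discharge, so constant hazard may understate early events.

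**The case against.** Several points on the other side stand.

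- **The rates are not irrelevant.** Attempts and hospitalization for suicidal risk are both components of the composite, and the study records suicidal events every two weeks. A reader might infer that 9.1 plans for outcomes the study will not measure. The documents do not support that; the fault is a different component in each arm.
- **The study is not shown to be underpowered.** At a fixed HR the composite gives more events and more power: with OCIC at 27.3%, about 0.7 power is reached near HR 2.0. Power is low only if the true HR is modest, and the documents cannot say whether it is.
- **The direction is not shown to be reversed.** A reader might set 19% against 27.3%, obtain an HR below 1, and conclude that inpatient care looks safer. That pairs readmission with a composite and so repeats the fault in 9.1. It is not evidence.
- **SA1 is not contradicted throughout.** SA1 makes no inpatient vs OCIC prediction, so the headline contrast does not oppose it. Opposition arises only for telehealth vs inpatient. For telehealth vs OCIC, equal rates assume no difference (9.1 separately mentions an HR below 2). The test is already two-sided and remains valid.
- **27.3% is not a firm planning value.** It comes from one site, from the 78.6% who responded (286/364), and is counted from discharge. Its listed components do not name interrupted attempts or death by suicide. Dallas runs a 4–6 week programme with groups, while the site descriptions for the other three give an average of 1–3 sessions. This argues for a range, not for keeping 10%.
- **The study calls itself a pilot and is observational.** That lowers the stakes, but a pilot that reports power should report it for its own endpoint.

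**Conclusion.** The concern holds as a fault in the planning basis. Section 9.1 compares readmission in one arm with attempts in the other, labels both as the same rate, and applies the result to a composite that is neither. The documents' only OCIC figure near the composite is almost three times the 10% used (27.3/10 = 2.7). On that figure, the assumed HR of 2 to 2.8 would require inpatient event rates of 47% to 59%, for which the documents offer no support.

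The HR of 2.8 is unsupported rather than refuted. If OCIC were near 12%, an inpatient rate of about 30% would give HR 2.8. Power for the unchanged sample runs from about 0.15 (OCIC 12%, HR 1.5) to 0.98 (OCIC 27.3%, HR 2.8), so a single value of 0.70 is not informative.

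The mismatch with SA1 is narrower but real: telehealth is planned as better than inpatient and equal to OCIC, and hypothesised as worse than both.

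These figures assume proportional hazards, the stated arm sizes of 70 and 75, and 6-month follow-up. The 12% also assumes constant hazard.

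**What to change.** In Section 9.1:
1. Put all three arms on the suicidal event defined in Section 2.2, with ranges marked as assumptions: for example OCIC about 12% to 27.3%, stating that the low end extrapolates ED returns only, and inpatient 20% to 50%.
2. Restate power, or the detectable HR, over those ranges for the unchanged sample.
3. Label the 10% as attempts and the 19% as readmissions wherever they are still cited.
4. Add power for telehealth worse than OCIC and worse than inpatient, as SA1 expects, or state that no direction is assumed.
5. Match the rates to the analysis window. 9.1 uses 6-month rates; Sections 4.2 and 9.2.3 describe a 3-month analysis.

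Carry the restated figures into Sections 4.2 and 9.2.3, which repeat the HR 2.8 power claim. The mismatch between HR 2.8 and the 19% and 10% rates can be settled in the same recalculation.

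The cost is one recalculation, a rewritten paragraph and two conforming edits. There is no change to sample size, endpoint or analysis model. The downside is that a single 0.70 gives way to a range that is lower at modest hazard ratios.

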Most Relevant Preliminary Data: In 2017, out of 401 adolescent patients with suicidality who were in the Cincinnati Children's Hospital's OCIC, only 25 (6%) returned to the ED for psychiatric reasons within 90 days of their first OCIC appointment. Also, the treatment satisfaction ratings by parents were higher for OCIC than inpatient in 2017. For example, significantly more parents (88%) rated that they felt that they participated as much as they should have in OCIC in comparison to inpatient psychiatry (74%). Upon completion of the Dallas OCIC, one of our four sites, teens and parents completed the Client Satisfaction Questionnaire (CSQ-8) CSQ to assess satisfaction. Both patient and parent satisfaction were very high. In response to the question, "In an overall, general sense, how satisfied are you with the service you have received?", 99% of parents and 96% of teens responded that they were mostly satisfied or very satisfied. When asked if they would refer a friend, 89% of parents and 67% of teens responded "definitely yes" while only 1% of parents and 2.3% of teens responded "don't think so". The average score across items on the CSQ for those who were enrolled in the program was 3.78 (SD=.33) for parent (n=290), and 3.54 (SD=.49) for teen (n=302) on a 4 point scale (with 4 indicating the highest level of satisfaction). The findings suggest that OCIC for adolescents with suicidality is both acceptable and feasible as well as efficacious as an alternative to inpatient psychiatry treatment. However, a randomized trial is needed in order to determine the efficacy of OCIC compared to inpatient psychiatry. At our site in Dallas, [name] saw 364 eligible adolescents (aged 12 to 17 years; mean age 14.9 ± 1.4 years) from January 1, 2014 and December 31, 2015 who had a worsening of suicidal ideation or a recent suicide attempt were enrolled in a newly-developed OCIC and attended at least 1 appointment. Suicidality (CHRT-SR) was assessed at baseline and discharge from the program. The majority of patients completed the OCIC program (81.04% over a 4 week period). Patients were improved at the time of discharge on depressive symptoms and suicidal ideation and behavior. Both parents and patients reported significant improvement in depression severity based on the QIDS-A at exit (7.67 ± 4.87 and 8.65 ± 5.58 , respectively) compared to baseline (13.22 ± 4.81 and 13.65 ± 5.98 , respectively), $p < .0001$.

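### Section 9.1 pairs a hazard ratio of 2.8 with 6-month rates of 19% and 10%, which imply 2.0; on those rates power is about 0.34 to 0.35, not 0.70

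*Combined protocol and SAP*

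**What the plan says.** Section 9.1 expects at least 75 telehealth, 75 OCIC and 70 inpatient patients, and adds: "These numbers account for an expected 10 % dropout rate". For inpatient versus OCIC the key sentence contains "if we assume the hazard ratio (inpatient group vs. OCIC group) will be approximately 2.8 and the readmission rates over 6 months". It puts those rates at 19% and 10% respectively and concludes that power is 0.70 with two-sided alpha 0.05. The 19% is introduced as an inpatient readmission rate. The 10% comes from unpublished site data, where "almost 10% of adolescents who received OCIC treatment following a suicidal event could have recurrent suicidal attempts" over 6 months.

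For telehealth the section says "We will achieve similar power when we compare the Telehealth CIS group with the inpatient group". It describes the whole calculation, done with the powerSurvEpi package in R, as "based on the assumption that 19% (inpatient group) vs. 10% (Telehealth CIS or OCIC group) will be the averaged recurrence rates" across sites.

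Sections 4.2 and 9.2.3 repeat the claim as power above 0.70 at a hazard ratio of 2.8. They refer to recurrence within 3 months and give no event rate.

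**The concern.** The hazard ratio and the two rates are not independent choices. Under proportional hazards, a pair of 6-month risks fixes the ratio, and 19% against 10% is well short of 2.8. The rates are stated to be the basis of the calculation, so they cannot be set aside as illustration.

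The figure of 0.70 is the power claimed for the primary time-to-event outcome, and the telehealth versus inpatient comparison, part of the safety aim, borrows it. If real power on the planned rates is half that, a non-significant result could be read as more reassuring than it is. As written, nobody can tell which rates or which effect the Cox comparison was planned to detect.

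**Working it through.** **Inputs (Section 9.1).** Inpatient n = 70, OCIC n = 75; 6-month risks 0.19 and 0.10; hazard ratio (HR) 2.8; two-sided alpha 0.05; stated power 0.70. The powerSurvEpi function is not named, so two standard formulas are used:

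- Freedman form: power = Φ(√(k·m)·|HR − 1|/(k·HR + 1) − 1.96), with k = 70/75.
- Schoenfeld: power = Φ(√(m·p(1 − p))·ln HR − 1.96), with p = 70/145.

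Here m is the expected number of events.

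**Step 1: reproduce the plan's figure.** m = 70 × 0.19 + 75 × 0.10 = 20.8. Taking HR 2.8 literally with these events gives 0.593 (Freedman) and 0.650 (Schoenfeld), so 0.70 is not reproduced. Schoenfeld reaches 0.704 at HR 2.8 with 81 per arm (m = 23.5), that is, before dropout. This may be where 0.70 came from.

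**Step 2: the HR that the rates imply.** ln(1 − 0.19)/ln(1 − 0.10) = 2.00. The risk ratio is 1.9 and the odds ratio 2.11, so no usual ratio of these rates gives 2.8. Conversely, HR 2.8 with OCIC at 10% needs an inpatient risk of 1 − 0.90^2.8 = 25.5%; with inpatient at 19% it needs an OCIC risk of 1 − 0.81^(1/2.8) = 7.2%.

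**Step 3: power on coherent inputs, 70 vs 75, 6 months.** The simulation is a log-rank test with exponential times, 20,000 runs.

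| Inpatient / OCIC | HR | Events | Freedman–Schoenfeld | Simulation |
|---|---|---|---|---|
| 19% / 10% | 2.0 | 20.8 | 0.336–0.352 | 0.34 |
| 25.5% / 10% | 2.8 | 25.4 | 0.679–0.736 | 0.70–0.71 |
| 19% / 7.2% | 2.8 | 18.7 | 0.549–0.605 | 0.57 |

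At HR 2.0, power of 0.70 needs about 52 (Schoenfeld) to 55 (Freedman, 54.3 rounded up) events, against 20.8 expected. With 81 per arm and no dropout, 19%/10% gives 0.365–0.390. A one-sided test on the planned arms gives at most 0.47.

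**Step 4: telehealth vs inpatient.** With telehealth at 10%, inpatient at 19% (n = 70) and telehealth n from 75 to 99, power is 0.34–0.39.

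**Step 5: do the rates describe the endpoint?** Section 2.2 defines the outcome broadly: "A suicidal event is defined as: a suicide attempt, interrupted attempt, hospitalization because of suicidal risk, an emergency/urgent evaluation because of suicidal risk", or death by suicide. A readmission rate and an attempt rate each cover only part of this. The protocol's own OCIC data vary widely. In Dallas, 27.3% of 286 respondents (of 364) had a suicidal event within 6 months. In Cincinnati, of 401 patients, "only 25 (6%) returned to the ED for psychiatric reasons within 90 days of their first OCIC appointment", which is not the full composite. Varying the OCIC rate, with events recalculated at each HR:

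| OCIC 6-month rate | Power at HR 2.0 | HR for 70% power | HR for 80% power |
|---|---|---|---|
| 10% | 0.34–0.35 | 2.7–2.9 | 3.0–3.2 |
| 15% | 0.46–0.48 | 2.4 | 2.6–2.7 |
| 20% | 0.57–0.59 | 2.2 | 2.3–2.4 |
| 27.3% | 0.69–0.72 | 2.0 | 2.1–2.2 |

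**Step 6: the 3-month horizon of Sections 4.2 and 9.2.3, HR 2.8.** With a constant hazard (half the 6-month cumulative hazard by 3 months), a 10% OCIC rate gives 0.42–0.47 and 27.3% gives 0.83–0.87. Using 25/401 = 6.2% at 90 days gives 0.49–0.54. The claim of more than 0.70 therefore depends on a rate that those sections do not state.

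**A slip in the same paragraph.** The ANOVA power of 0.76 (three groups, n = 220) belongs to f = 0.2, that is f² = 0.04, which gives 0.755. The printed f² = 0.2 gives more than 0.999.

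**The case against.** The documents do not say which input is wrong. Half the stated power follows only if the rates are kept and the hazard ratio dropped. Keeping HR 2.8 gives 0.55–0.61 or 0.68–0.74, depending on which rate is moved, and the literal mixture gives 0.59–0.65. This is fair, and the fix leaves the choice open. But the plan names 19% and 10% as the basis of its calculation, the literal mixture also misses 0.70, and the pre-dropout route to 0.704 ignores an allowance the section says is already made and keeps the incompatible ratio.

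The rates are also rounded. With the Dallas attempt rate of 8.7% in place of 10%, the implied HR is 2.3 and power 0.43–0.46. That widens the range but does not approach 0.70.

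As neither rate is a composite-event rate, 0.34 is not an estimate of the study's real power. This stands. At HR 2.0 with OCIC at 27.3%, power is 0.69–0.72, though that implies about 47% of inpatients having an event (1 − 0.727² = 0.471).

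The constant-hazard 3-month figures are open to challenge, because Section 2.2 reports that almost half of reattempts came within a month of discharge. If, for illustration, 70% of the cumulative hazard fell by 3 months, the 10% case would give 0.54–0.60. This too stands, and it is a further reason to state the assumption.

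Finally, Sections 4.2 and 9.2.3 call the study a pilot, it is observational, and it openly claims modest power. None of that makes a stated power agree with inputs that do not deliver it.

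**Conclusion.** The concern holds and must be fixed. The rates of 19% and 10% imply a hazard ratio of 2.0, and with 70 and 75 patients they give about 21 events and power of 0.34–0.35 against the stated 0.70. The similar-power statement for telehealth versus inpatient fails for the same reason. The claim in Sections 4.2 and 9.2.3 is not wrong in itself, but 19% and 10% cannot support it.

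This rests on proportional hazards, as the planned Cox model assumes, on reading the two rates as cumulative 6-month risks, and on arm sizes already net of dropout. It establishes that the justification is incoherent, not that power for the composite endpoint is 0.34.

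**What to change.** In Section 9.1, use one coherent set of rates and hazard ratio and restate the power.

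- If 19% and 10% are kept, for example: *These rates correspond to a hazard ratio of 2.0. With 70 and 75 patients, about 21 events are expected by 6 months and power is about 0.34–0.35. With a 10% OCIC rate, the detectable hazard ratio is about 2.7–2.9 for 70% power and 3.0–3.2 for 80% power, with events recalculated at each ratio.*
- If 2.8 is kept with a 10% OCIC rate, state and justify the inpatient rate it needs, about 25.5%.

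Revise the telehealth versus inpatient sentence to match. In Sections 4.2 and 9.2.3, give the event rates and horizon behind the power figure and reconcile 3 with 6 months. Show power over a range of composite-event rates for every arm, for example 10% to 27.3%, without fixing OCIC at either end. Name the powerSurvEpi function used. Correct f² = 0.2 to f = 0.2 (f² = 0.04).

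The cost is one recalculation and wording in three sections, with no extra patients or visits. If 19% and 10% are kept, the stated power becomes less favourable.
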